1. SYNOPSIS

Name of Sponsor: Sunovion Pharmaceuticals Inc.

Name of Investigational Product: Dasotraline (SEP-225289)

Title of Study: An Open-label, Flexibly-dosed, Multicenter, Extension Study of Dasotraline to Evaluate Long-term Safety and Tolerability in Adults with Binge-eating Disorder

Proposed Indication: Binge-eating Disorder

Study Centers: ~ 61 clinical sites in the United States

Planned Study Period: 35 months

Study Objectives:

Primary: To evaluate the long-term safety and tolerability of flexibly-dosed dasotraline (4, 6, or 8 mg/day) in adults with binge-eating disorder (BED) who have completed a prior dasotraline study in BED by:

- The incidence of adverse events (AEs), discontinuations due to AEs, and serious AEs (SAEs)
- The frequency and severity of suicidal ideation and suicidal behavior using the Columbia Suicide Severity Rating Scale (C-SSRS)
- Changes in 12-lead electrocardiograms (ECGs), vital signs, body weight, body mass index (BMI), and clinical laboratory results

Secondary:

- To assess potential withdrawal effects of dasotraline using the following assessments (administered during the withdrawal period):
 - Cocaine Selective Severity Assessment (CSSA)
 - Discontinuation-Emergent Signs and Symptoms (DESS) Scale
 - Symptoms of anxiety utilizing the Hamilton Anxiety Rating Scale (HAM-A)
 - Symptoms of depression utilizing the Montgomery-Asberg Depression Rating Scale (MADRS)
- To assess the abuse potential of dasotraline utilizing a comprehensive abuse potential monitoring plan (APMP)
- To evaluate the long-term effectiveness of flexibly-dosed dasotraline in the treatment of adults with BED as measured by the following:
 - Eating Disorder Examination Questionnaire (EDE-Q) modified
 - Binge-eating Clinical Global Impressions Severity (BE-CGI-S)

- Sheehan Disability Scale (SDS)
- To assess subject-reported health status using the Medical Outcomes Study 12-Item Short Form Survey Instrument (SF-12)¹

Study Design: This is a Phase 3, 12-month, multicenter, open-label, flexibly-dosed, safety study in adults with BED. This study is projected to enroll approximately 500 subjects based on the number of subjects expected to complete treatment in the core studies (ie, SEP360-221 or SEP360-321).

Informed consent will be obtained from all subjects after all procedures from the core study have been completed and before any study procedures unique to this study are performed. Safety and tolerability will be monitored throughout the study by AE reports, physical and neurological examinations, 12-lead ECG, vital signs, body weight, BMI, clinical laboratories (hematology, chemistry, urinalysis, hemoglobin A1c, and lipid panel), and C-SSRS. Effectiveness will be evaluated using the BE-CGI-S, EDE-Q modified, and SDS. Subject-reported health status will be assessed using the SF-12 (subjects from Study SEP360-221 only). Assessment of potential withdrawal effects of dasotraline will be conducted via administration of the CSSA, DESS, HAM-A, and MADRS at the end of treatment and during the 3-week study medication withdrawal period.

A comprehensive Abuse Potential Monitoring Plan (APMP; see Section 24) for dasotraline designed to detect potential abuse of the compound and to more closely monitor AEs consistent with the known pharmacology for dasotraline will be implemented.

An independent Data and Safety Monitoring Board (DSMB) will review safety data including data on adverse events (AEs) and serious adverse events (SAEs) at regular intervals.

Subjects will self-administer study drug on an outpatient basis for 12 months, once a day at approximately the same time each morning with or without food, including on the days when clinic visits occur. Subjects meeting all inclusion and no exclusion criteria will start taking open-label study drug on Day 1, the morning following the OL Baseline visit (ie, Week 12 visit in the core study).

The total daily dose will remain between 4 mg/day and 8 mg/day for the 12-month treatment period. Dasotraline will be dosed at 4 mg/day for the first 2 weeks of the study. At the Week 2 visit, the dose may be increased to 6 mg/day. Thereafter the dose may be increased or decreased by 2 mg/day, as necessary for effectiveness or tolerability reasons at the discretion of the investigator. A minimum of 8 days is required between dose increases. Dose decreases may be made at less than 8 day intervals, at the investigator's discretion, for reasons of safety or tolerability. If, in the judgment of the investigator, the subject does not tolerate the minimum required dose (4 mg/day), he or she will be discontinued from the study.

All changes in study drug dose will begin the morning after the visit at which the dose change decision is made and using the new package of study drug.

The study will consist of a baseline visit, 12-month open-label treatment period, and 3-week study drug withdrawal period as shown in the Study Schematic (Figure 1). During the treatment period, subjects will return to the clinic at the end of 2 and 4 weeks for clinical evaluation and thereafter will return to the clinic once every 4 weeks during the treatment period for scheduled visits. At the approximate midpoint between the scheduled monthly visits (ie, 14 ± 2 days after a visit), the site staff will contact the subject via telephone, text, or email in order to monitor for SAEs, AEs, and concomitant medications, as well as to remind subjects about adherence to study drug administration, and upcoming visits. If necessary, an unscheduled visit can be arranged.

¹ SF-12 collected only for subjects enrolling in this study after completing core Study SEP360-221.

Subjects will attend weekly visits during the 3-week study drug withdrawal period. Assessment of potential withdrawal effects will be conducted via administration of the CSSA, DESS, HAM-A, and MADRS at the end of treatment. Subjects will undergo assessments every other day and weekly as follows: the CSSA and DESS will be completed every other day during the 3-week study medication withdrawal period. Clinical site staff will call the subject every other day, beginning the second day after the last dose of study drug, unless a clinic visit is scheduled for that day. Phone contacts may be made up to 3 times per day if the clinical site staff is unable to contact the subject on the first 2 attempts. If the subject cannot be contacted on a given day, during the next contact the study site staff will retrospectively collect the missed CSSA and DESS, in addition to the current day's CSSA and DESS, as necessary. Clinical site staff will record the responses in the subject's source information and in the CRF with the contact date and time. The CSSA, DESS, HAM-A, and MADRS also will be administered at each weekly visit during the withdrawal period.

A window of ± 1 day will be allowed for each weekly clinic visit and telephone call during the study medication withdrawal period.

After the last withdrawal period visit, all subjects will be referred for follow-up care as determined by the investigator.

Number of Subjects (planned): This study is projected to enroll approximately 500 subjects based on the number of subjects expected to complete treatment in the core studies.

Diagnosis and Main Criteria for Subject Inclusion:

Inclusion Criteria:

- 1. Completion of the treatment period of a dasotraline core study (ie, SEP360-221 or SEP360-321) for the treatment of BED.
- 2. Subject has agreed to participate by providing written informed consent and is willing and able to comply with the protocol, in the opinion of the investigator.
- 3. Subject has not taken any medication other than the study drug for the purpose of controlling BED symptoms during the core study.
- 4. Female subject must have a negative urine pregnancy test at open-label (OL) Baseline; females who are post-menopausal (defined as at least 12 months of spontaneous amenorrhea) and those who have undergone hysterectomy or bilateral oophorectomy will be exempted from the pregnancy test.
- 5. Female subject of childbearing potential and male subject with female partner of childbearing potential must agree to use an effective and medically acceptable form of birth control (see Section 22, Appendix III) throughout the study period. Note: Continued use of an effective and medically acceptable form of birth control is recommended for 30 days after study completion.
- 6. Subject is judged by the investigator to be suitable for participation in a 12-month clinical trial involving open-label dasotraline treatment.
- 7. Subject can read well enough to understand the informed consent form and other subject materials.

Exclusion Criteria:

- 1. Subject is considered by the investigator to be at imminent risk of suicide, injury to self or to others, or damage to property.
- 2. Subject is considered a suicide risk in the investigator's opinion or has any previous history of suicide attempt within the past 12 months.
- 3. Subject answers "yes" to "suicidal ideation" item 4 (active suicidal ideation with some intent to act, without specific plan) or item 5 (active suicidal ideation with specific plan and intent) on

the C-SSRS assessment at OL Baseline. Subjects who answer "yes" to this question must be referred to the Investigator for follow-up evaluation.

- 4. Subject has a clinically significant abnormality including physical examination, vital signs, ECG, or laboratory tests that the investigator in consultation with the medical monitor considers to be inappropriate to allow participation in the study.
- 5. Subject has a positive urine drug screen (UDS) or breath alcohol test at OL Baseline.
- 6. Subject is breastfeeding.
- 7. Subject is at high risk of non-compliance in the investigator's opinion.

Investigational Product, Dosage and Mode of Administration:

Dasotraline 4 mg, 6 mg, and 8 mg capsules for oral administration will be supplied. Based on the flexible dosing schedule, 1 capsule of dasotraline 4 mg, 6 mg, or 8 mg will be taken once daily, at approximately the same time each morning with or without for food. Following the initial 2 weeks at 4 mg, subjects will be flexibly dosed at 4, 6, or 8 mg/day for the duration of the study.

Dose schedule and adjustment are described above under Study Design.

Duration of Treatment: 12 months

Reference Therapy, Dosage and Mode of Administration: Not applicable

Concomitant Medications:

Use of certain medications, including but not limited to the following, is prohibited throughout the study from open-label baseline through the 3-week study medication withdrawal period:

- psychostimulants
- any medications for the treatment of binge eating or other eating disorders, obesity, or weight gain
- antidepressant medications (eg, bupropion, SSRI/SNRI, Monoamine oxidase [MAO] inhibitor, tricyclic) and St. John's Wort
- medications that are CYP2B6 substrates or inhibitors or inducers of CYP2B6, eg, bupropion, cyclophosphamide, carbamazepine, etc (see Section 23, Appendix IV)
- medications for the treatment of attention deficit hyperactivity disorder (ADHD)
- corticosteroids except as noted in Section 10.3.3 and anabolic steroids
- antiepileptic medications
- benzodiazepines except for sleep or anxiety
- mood stabilizers (eg, lithium, anticonvulsants)
- antipsychotic medications
- suvorexant
- any medication that can result in either weight gain or weight loss (eg, insulin, liraglutide, diphenhydramine except topical formulations, etc) including over-the-counter and herbal products

Use of concomitant medications permitted during the study include, but are not limited to, sleep aids (with some restrictions), anxiety (with some restrictions), oral contraceptives, and limited use of

opiates.

Other Restrictions: Participation in non-pharmacologic therapy such as supportive psychotherapy, cognitive behavioral therapy or interpersonal therapy is permitted and should be documented by the investigator, to the extent possible. Any participation in a formal weight loss program such as Weight Watchers® is prohibited throughout the study.

See Section 10.3 for complete information on concomitant medications and therapies permitted during the study.

Study Endpoints:

Safety Endpoints:

- The incidence of overall AEs, serious AEs (SAEs), and AEs (or SAEs) leading to discontinuation
- Clinical laboratory evaluations (serum chemistry, hematology, urinalysis)
- Clinical evaluations (vital signs including orthostatic effects, and 12-lead ECGs)
- Frequency and severity of suicidal ideation and suicidal behavior using the C-SSRS
- Change and percent change in body weight and BMI
- Change in fasting lipid panel (triglycerides, total cholesterol, high-density lipoprotein [HDL] cholesterol, and low-density lipoprotein [LDL] cholesterol)
- Change in hemoglobin A1c levels
- Change in fasting glucose levels
- Change in the symptoms of withdrawal from dasotraline from Week 52/EOT as measured by:
 - CSSA total score at Weeks 53, 54, and 55
 - DESS total score at Weeks 53, 54, and 55
 - HAM-A total score at Weeks 53, 54, and 55
 - MADRS total score at Weeks 53, 54, and 55

Effectiveness Endpoints:

- Change in EDE-Q modified global score and subscale scores (restraint, shape concern, weight concern), and Items 4-6 scores
- Change in BE-CGI-S score
- Change in SDS total score and subscale scores (school/work disability, social life disability, and family life disability)

Subject-reported Health Status Endpoints:

• Change in SF-12 two component scores (physical component, mental health component)²

Statistical Methods:

The safety population will include all subjects who receive at least one dose of study medication. A total of 2 analysis groups will be formed based on a subject's previous participation in the core study (previously randomized to dasotraline, previously randomized to placebo). A group that combines these 2 analysis groups also will be presented. Summary tables, wherever applicable, will be presented by analysis group, respectively. Where changes are reported, the reference will be to the pretreatment baseline from the core study, and indicated as "DB baseline". Where relevant, changes from baseline for the open-label study, defined as the Week 12 assessment in the double-blind study or the last assessment prior to the first dose of study medication in the open-label study, will also be reported, and will be referred to as the open-label study baseline or "OL baseline." Continuous variables will be summarized using descriptive statistics (N, mean, standard deviation, median, range, 95% confidence interval [CI] as needed) and categorical variables will be reported as frequencies and percentages. No statistical comparisons will be conducted and no inferential statistics on effectiveness and safety will be presented.

Safety Analyses: The safety data will be analyzed by analysis group based on the safety population for the open-label treatment period (for data up to the end of treatment period) and withdrawal period (for data collected during the withdrawal period), separately, as appropriate.

Treatment-emergent adverse event (TEAE) and discontinuation-emergent adverse events (DEAE) will be summarized (hereafter TEAE is referred as AE). The incidence of AEs, SAEs, and AEs leading to discontinuation due to AEs (or SAEs) will be summarized by analysis group (by presenting the number and percentage of subjects with one or more AEs in each category). The number and proportion of subjects with one or more AEs within a system organ class (SOC) or by preferred term will be presented by analysis group as well.

For laboratory tests (hematology, chemistry, urinalysis, lipid panel, hemoglobin A1c), weight, BMI, vital signs, neurological examination, and ECG parameters, descriptive statistics will be provided for observed values and changes from DB baseline and OL baseline for the continuous variables. Frequencies and percentages will be reported for categorical variables by study visit and analysis group. The markedly abnormal values for selected safety parameters will be summarized, as appropriate.

The number and percentage of subjects with suicidal ideation and/or suicidal behavior, emergence or worsening of suicidal ideation or suicidal behavior will be summarized by analysis group for the open-label treatment period, and the withdrawal period, separately.

The CSSA total score, DESS total score, MADRS total score, and HAM-A total score will be summarized by presenting descriptive statistics of observed values and changes from Week 52/EOT by treatment and visit for the withdrawal period.

Analyses for Effectiveness and Subject-reported Health Status: Descriptive statistics of observed values and changes from DB baseline and OL baseline in BE-CGI-S score, EDE-Q modified global and subscale scores (restraint, shape concern, weight concern), EDE-Q modified items 4-6 scores, SDS total score and subscale scores (school/work disability, social life disability, and family life disability), and SF-12 (subjects from Study SEP360-221) two component scores (physical component, mental

² SF-12 collected only for subjects enrolling in this study after completing core Study SEP360-221.

health component) will be summarized by visit and analysis group.

Sample Size: Subjects who complete the double-blind treatment period of the core study, sign the informed consent, and meet all entry criteria will be included in this study. The double-blind core study SEP360-221 plans to randomize approximately 300 subjects and the double-blind core study SEP360-321 plans to randomize approximately 480 subjects. It is estimated that approximately 500 subjects will be eligible for enrollment in this study based on the number of subjects expected to complete treatment in the core studies.

Table 2:Schedule of Assessments

						Treatme	nt Period				
	V1E OL BSN ^a	V2E Week 2	V3E Week 4	V4E Week 8	V5E Week 12	V6E Week 16	V7E Week 20	V8E Week 24	V9E Week 28	V10E Week 32	V11E Week 36
		Dav	Dav	Dav	Dav	Dav	Dav	Dav	Dav	Dav	Dav
Procedures	Day -1	14 ± 3	28 ± 3	56 ± 3	84 ± 3	112 ± 3	140 ± 3	168 ± 3	196 ± 3	224 ± 3	252 ± 3
Informed Consent ^e	Х										
Inclusion/Exclusion Criteria	Х										
Dispense Study Drug ^c	Х	Х	Х	Х	Х	Х	Х	Х	Х	Х	Х
Study Medication Accountability		Х	Х	X	X	X	X	Х	X	Х	X
Between visit contact ^d			At the approximate midpoint between Visits 3E and 4E, Visits 4E and 5E, Visits 5E and 6E, Visits 6E and 7E, Visits 7E and 8E, Visits 8E and 9E, Visits 9E and 10E, Visits 10E and 11E, and Visits 11E and 12E								
Demographics	Х										
Physical Examination	X (carried over)				Х			Х			
Neurological Examination	X (carried over)							Х			
Prior and Concomitant Medications	X (carried over)	Х	Х	Х	Х	Х	X	Х	X	Х	Х
Binge-eating Clinical Global Impressions of Severity (BE-CGI-S)	X (carried over)		Х	Х	Х	Х	Х	Х	Х	Х	Х
Eating Disorder Examination Questionnaire (EDE-Q) modified	X ¹		X	X	X	X	X	X	X	X	X
Sheehan Disability Scale (SDS)	X (carried over)				X			Х			Х

						Treatme	nt Period				
	V1E	V2E	V3E	V4E	V5E	V6E	V7E	V8E	V9E	V10E	V11E
	OL BSN ^a	Week 2	Week 4	Week 8	Week 12	Week 16	Week 20	Week 24	Week 28	Week 32	Week 36
		Day	Day	Day	Day	Day	Day	Day	Day	Day	Day
Procedures	Day -1	14 ± 3	28 ± 3	56 ± 3	84 ± 3	112 ± 3	140 ± 3	168 ± 3	196 ± 3	224 ± 3	252 ± 3
Medical Outcomes Study 12-Item Short Form Survey Instrument (SF-12) for subjects from Study SEP360-221 only	X (carried over)				X			X			X
Vital Sign Measurements	X (carried over)	Х	Х	Х	Х	Х	Х	Х	Х	X	X
Weight and Body Mass Index	X (carried over)	Х	Х	Х	X	Х	Х	Х	Х	X	X
Height	X (carried over)										
Adverse Events	X (carried over)	Х	Х	Х	Х	Х	Х	Х	Х	Х	Х
Serum chemistry ^f	X (carried over)				Х			Х			X
Lipid panel ^f	X (carried over)				X			Х			X
Hemoglobin A1c	X (carried over)				X			Х			X
Hematology	X (carried over)				X			Х			X
Urinalysis	X (carried over)				X			X			X
Columbia – Suicide Severity Rating Scale (C-SSRS) ^g	X (carried over)	Х	Х	X	X	Х	Х	Х	Х	Х	X

Table 2:Schedule of Assessments (Continued)

			Treatment Period								
	V1E	V2E	V3E	V4E	V5E	V6E	V7E	V8E	V9E	V10E	V11E
	OL BSN ^a	Week 2	Week 4	Week 8	Week 12	Week 16	Week 20	Week 24	Week 28	Week 32	Week 36
		Day	Day	Day	Day	Day	Day	Day	Day	Day	Day
Procedures	Day -1	14 ± 3	28 ± 3	56 ± 3	84 ± 3	112 ± 3	140 ± 3	168 ± 3	196 ± 3	224 ± 3	252 ± 3
Hamilton Anxiety Rating Scale (HAM-A) ^h	X (carried over)							Х			
Montgomery-Asberg	X (carried							Х			
Depression Rating Scale (MADRS) ⁱ	over)										
Cocaine Selective											
Severity Assessment											
(CSSA) ^J											
Discontinuation-											
Emergent Signs and											
Symptoms (DESS)											
Scale'	T () 1		37								
Urine Pregnancy Test	X (carried		Х		X		Х		Х		Х
(temales of child-	over)										
bearing potential only)	X 7 (1		V		N/		V		N		V
Urine Drug Screen	X (carried		Х		X		Х		Х		Х
	over)		V		V		V		V		V
Breath Alcohol Test	X (carried over)		Х		X		Х		Х		Х
12-Lead	X (carried		Х		Х			Х			Х
Electrocardiogram	over)										
(ECG)											

Table 2:Schedule of Assessments (Continued)

		Treatme	nt Period	Withdrawal Period				
	V12E	V13E	V14E	V15E/EOT	V16E	V17E	V18E/EOS	
	Week 40	Week 44	Week 48	Week 52 ^b	Week 53	Week 54	Week 55	
	Day	Day	Day	Day	Day	Day	Day	
Procedures	280 ± 3	308 ± 3	336 ± 3	364 ± 1	371 ± 1	378 ± 1	385 ± 1	
Informed Consent ^e								
Inclusion/Exclusion Criteria								
Dispense Study Drug ^c	Х	Х	Х					
Study Medication Accountability	Х	Х	Х	Х				
Between visit contact ^d	At the appr Visi	oximate midpoint ts 13E and 14E, a	between Visits 12 nd Visits 14E and	2E and 13E, 15E.				
Demographics				-				
Physical Examination				Х			X	
Neurological Examination				Х			Х	
Prior and Concomitant	Х	Х	Х	Х	Х	Х	Х	
Medications								
Binge-eating Clinical Global	Х	Х	Х	Х	Х	Х	Х	
Impressions of Severity								
(BE-CGI-S)								
Eating Disorder Examination	Х	Х	Х	Х				
Questionnaire (EDE-Q) modified								
Sheehan Disability Scale (SDS)				Х			Х	
Medical Outcomes Study 12-Item				Х			Х	
Short Form Survey Instrument								
(SF-12) for subjects from Study								
SEP360-221 only								
Vital Sign Measurements	Х	Х	Х	Х	Х	X	Х	
Weight and Body Mass Index	Х	Х	Х	Х	Х	Х	Х	
Height								
Adverse Events	Х	Х	Х	Х	Х	Х	X	
Serum chemistry ¹				Х			X	
Lipid panel ¹				Х			X	
Hemoglobin A1c				Х			Х	
Hematology				Х			Х	

Table 2:Schedule of Assessments (Continued)

		Treatme	ent Period		Withdrawal Period			
	V12E	V13E	V14E	V15E/EOT	V16E	V17E	V18E/EOS	
	Week 40	Week 44	Week 48	Week 52 ^b	Week 53	Week 54	Week 55	
	Day	Day	Day	Day	Day	Day	Day	
Procedures	280 ± 3	308 ± 3	336 ± 3	364 ± 1	371 ± 1	378 ± 1	385 ± 1	
Urinalysis				X			X	
Columbia – Suicide Severity Rating Scale (C-SSRS) ^g	Х	X	X	Х	Х	X	Х	
Hamilton Anxiety Rating Scale (HAM-A) ^h				Х	Х	X	Х	
Montgomery-Asberg Depression Rating Scale (MADRS) ⁱ				Х	Х	Х	Х	
Cocaine Selective Severity Assessment (CSSA) ^j				Х	Х	X	Х	
Discontinuation-Emergent Signs and Symptoms (DESS) Scale ^j				X	Х	X	Х	
Urine Pregnancy Test ^k (females of child-bearing potential only)	Х	Х	Х	Х			X	
Urine Drug Screen		Х		X			X	
Breath Alcohol Test		Х		X			X	
12-Lead Electrocardiogram (ECG)				X	X	X	X	

Table 2: Schedule of Assessments (Continued)

Abbreviations: BSN = baseline; EOS = End of Study; EOT = End of Treatment; OL = open label; V = visit

^a Week 12 in core study. Baseline assessments indicated as "carried over" are primarily performed as part of Week 12 visit in the core study and do not need to be repeated; the data will be duplicated from Week 12 visit or other visits (such as for height) in the core study.

^b Subjects who discontinue from the study prior to completion of treatment with study drug will be asked to return to the site and complete the EOT assessments within 1 day of discontinuation and complete the Withdrawal Period visits and calls.

^c Subjects will take the first dose of study drug in this study on Day 1 (the morning following the baseline visit); there will be no break in study drug treatment between the core study and this extension study. All study drug will be administered by the subject once a day at approximately the same time each morning including on the days when clinic visits occur.

^d At the approximate midpoint between the scheduled monthly treatment period visits (ie, 14 ± 2 days after a visit), the site staff will contact the subject via telephone, text, or email to monitor for SAEs, AEs, and concomitant medications, as well as to remind subjects about adherence to study drug administration and upcoming visits, following which an unscheduled visit may be scheduled, if necessary.

Footnotes continued on the next page.

- ^e Informed consent will be obtained from all subjects after all procedures from the core study have been completed and before any study procedures unique to this study are performed.
- ^f Subjects must be fasting for at least 8 hours (may have water) prior to the indicated laboratory tests. Visits should be scheduled in the morning.
- ^g The "Since Last Visit" version will be used. Subjects who answer "yes" to "suicidal ideation" item 4 (active suicidal ideation with some intent to act, without specific plan) or item 5 (active suicidal ideation with specific plan and intent) on the C-SSRS assessment at any time during the study must be referred to the Investigator for follow up evaluation.
- ^h The Structured Interview Guide for the HAM-A (SIGH-A) will be used for the administration of the HAM-A.
- ⁱ The Structured Interview Guide for the MADRS (SIGMA) will be used for the administration of the MADRS.
- ^j Clinical site staff will call the subject every other day (± 1 day) during the study medication withdrawal period, beginning the second day after the last dose of study drug (unless a clinic visit is scheduled for that day) in order to collect the Cocaine Selective Severity Assessment (CSSA) and Discontinuation-Emergent Signs and Symptoms (DESS). Clinical site staff may call up to 3 times per day if the clinical site staff are unable to contact the subject on the first 2 attempts. If the subject cannot be contacted on a given day, during the next contact the study site staff will retrospectively collect the CSSA and DESS from the missed day(s) and the current day, as necessary.
- ^k Any positive urine β -hCG test should be confirmed by serum β -hCG.

¹Carried over for subjects enrolling in this study from SEP360-321 and collected for subjects enrolling in this study from SEP360-221.

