11.2.6.2. Cocaine Selective Severity Assessment (CSSA)

The CSSA (Kampman-1998) is a clinician-administered scale designed to evaluate withdrawal signs and symptoms related to stimulants over the past 24 hours. It takes approximately 10 minutes to administer the 18-item scale.

Included in the CSSA are those symptoms most often associated with early cocaine abstinence, including change in appetite, depression, fatigue, anhedonia, anxiety, irritability, sleep disturbance, and inability to concentrate, paranoia, carbohydrate craving, bradycardia, and suicidality. The CSSA is scored as follows: cocaine craving scores are obtained by having subjects record the highest intensity and frequency of cocaine craving experienced during the preceding 24 hours using visual analog scales. All items except item 14, are scored 0 to 7 according to instructions on the CSSA generally with 0 = no symptoms and 7 = maximum score on any individual item. Item 14 is scored 0 to 8 with 0 = no symptoms and 8 = maximum score. Heart rate is determined by radial pulse measurement.

On non-clinic days, the CSSA will be completed by site staff during a call to the subject.

In order to complete the visual analog scale (VAS) portion of the CSSA on days when there are no scheduled clinic visits, subjects will be provided with copies of the VAS in advance, and will record their response at the time of scale administration.

In order to complete the radial pulse portion of the CSSA on days when there are no scheduled clinic visits, subjects will measure their own radial pulse and provide the measurement to the site staff over the phone.

For consistency of radial pulse measurements, subjects also will take their own radial pulse for the CSSA completed during in-clinic visits.

Subjects will be instructed by the site staff regarding the appropriate way to take their pulse.

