15.3.3.4. Physical Dependence and Withdrawal Symptoms

For continuous data used to assess physical dependence and withdrawal symptoms (ie, CSSA total score, DESS total score, MADRS total score, and HAM-A total score), descriptive statistics of the observed values and changes from Week 52 Endpoint will be summarized by analysis group and visit for the withdrawal period.

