7.4.6.2. Withdrawal Period

MADRS total score, HAM-A total score, and each of the individual item scores in the withdrawal period will be summarized by presenting descriptive statistics (N, mean, median, and range) of observed values and change from DB baseline, OL baseline, and withdrawal baseline by analysis group and visit; a similar analysis will be performed by gender as well.

CSSA total score, DESS total score, and the individual scores will be summarized by presenting descriptive statistics (N, mean, median, and range) of observed values and change from withdrawal baseline by analysis group and visits based on the withdrawal population; the visits will be displayed in an order defined as follow: withdrawal Baseline, day 1-2, day 3-4, day 5-6, day 7-8, withdrawal Week 1, day 9-10, day 11-12, day 13-14, withdrawal Week 2, day 15-16, day 17-18, day 19-20, day 21-22, withdrawal Week 3. See [Section 6.1.2.2](#) for details about how to define these analysis visits per both clinic and non-clinic visits. A similar analysis will be performed by gender as well. Number and percentage of subjects with a new symptom or worsen old symptom for each DESS individual score (ie, each individual score of DESS with value of 1) by study visit and the worst case during the withdrawal period will be summarized based on the withdrawal population as well.

The number and percentage of subjects in each of the following breakdown will be summarized by study visit during the withdrawal period.

- CSSA total score: 0-7, 8-15, 16-30, 31-45, 46-60, >60;
- DESS total score category 1: 0-2, 3-5, 6-10, 11-15, 16-20;
- DESS total score category 2: 0-10, 11-20, 21-30, 31-43.

In addition, the number and percentage of subjects with change in DESS total score from withdrawal baseline by withdrawal visit and during any time point of the withdrawal period (per the worst case value) will be summarized in each of the following categories: ≤ 0 , +1, +2, +3, $\geq +4$.

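### SAP 7.4.6.2 gives the CSSA no per-subject worst-case summary, so its tables cannot say how many subjects ever had a rise after the last dose

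*Protocol*

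**What the plan says.** Protocol Synopsis and Section 6.1 define the withdrawal endpoints as change from Week 52/EOT at the three weekly visits, including "CSSA total score at Weeks 53, 54, and 55". Protocol 15.3.3.4 plans that "descriptive statistics of the observed values and changes from Week 52 Endpoint will be summarized by analysis group and visit for the withdrawal period".

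SAP 7.4.6.2 goes further and includes the phone-contact windows. The CSSA receives two kinds of output:

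- "CSSA total score, DESS total score, and the individual scores will be summarized by presenting descriptive statistics (N, mean, median, and range) of observed values". The same statistics are planned for change from Withdrawal Baseline. All are by analysis group and visit, and repeated by gender.
- Counts in score bands, introduced by "The number and percentage of subjects in each of the following breakdown will be summarized by study visit during the withdrawal period". The CSSA bands are "CSSA total score: 0-7, 8-15, 16-30, 31-45, 46-60, >60".

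The DESS gets both of these. It also gets each item at its worst during the withdrawal period, and a categorical table of "change in DESS total score from withdrawal baseline by withdrawal visit and during any time point of the withdrawal period (per the worst case value".

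Protocol 11.2.6.2 describes the CSSA as designed to "evaluate withdrawal signs and symptoms related to stimulants over the past 24 hours". Under SAP 5.3.2 both scales are collected by calls every other day for three weeks and at the weekly visits. Withdrawal Endpoint (SAP 6.1.4.2) is the last value, not the worst.

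**The concern.** Withdrawal effects are the first secondary objective, and the CSSA is the scale aimed at stimulant-type withdrawal. Each administration looks back one day, which is why it is repeated so often. A schedule of that kind can answer a per-subject question: how many people had a rise at any time after stopping? The planned CSSA tables answer a different one, namely what the group looked like at each contact. If reactions peak on different days, a group table shows only a slice of them at any contact. The SAP asks the per-subject question of the DESS and gives no reason for not asking it of the CSSA.

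**Working it through.** **The plan's own figure.** The CSSA has 18 items, 17 scored 0-7 and one scored 0-8: 17 × 7 + 8 = 127, which matches the range in SAP 5.3.2.1. The documents give no sample size, effect size or variance for the CSSA, so everything quantitative below is illustration.

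**Outputs side by side (SAP 7.4.6.2).**

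| Output | CSSA | DESS |
|---|---|---|
| Score and change, by visit (N, mean, median, range) | yes | yes |
| Bands of absolute score, by visit | yes | yes |
| Per-subject change categories, by visit | no | yes |
| Per-subject worst change over the period | no | yes |
| Items at worst over the period | no | yes |

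**Why the by-visit tables cannot be combined.** The share of subjects who ever rose lies between the largest by-visit share and the sum of the by-visit shares. If 5% rise at each of 12 assessments, the share who ever rose could be 5% (the same people each time) or up to 12 × 5% = 60% (different people each time). The bands do not help: a subject at 20 before and after stopping falls in the same 16-30 row as one who went from 5 to 20.

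**Assessment days.** Calls on Days 2, 4, …, 20 (10 days, including Day 14) plus clinic visits on Days 7 and 21 give nominally 12.

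**Is spread-out timing plausible?** Protocol 4.2 gives mean half-lives of 47.1 to 77.0 hours. Five half-lives are 5 × 47.1 / 24 = 9.8 days to 5 × 77.0 / 24 = 16.0 days. Different peak days are therefore possible, but the documents give no onset distribution.

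**Size under assumed reactions.** Let r be the share reacting, D the rise in points and c the share of reactors in their rise at a given visit. The expected mean change at that visit is r × D × c. Take r = 20%, D = 20 and a 4-day rise.

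- Onset uniform on Days 1-17: c is at most 4/17 = 0.235 and averages 38/(17 × 12) = 0.186. The expected mean change averages 0.2 × 20 × 0.186 = 0.75 and is at most 0.94. Weeks 53-55 together catch 8/17 = 47% of reactors; the 12 assessments catch all of them.
- Onset uniform on Days 3-7: c peaks at 4/5 = 0.80, giving 0.2 × 20 × 0.80 = 3.2.

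Simulation with 300 subjects and a noise SD of 4 per assessment takes the largest of the 12 noisy visit means. It gives about 1.4 for spread onset and about 3.4 for clustered onset. The share with a rise of 10 or more is 7.3% at a typical visit with spread onset and about 20% at the peak visit with clustered onset. Noise alone gives 3.8% at a typical visit.

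For reactions of 1 to 3 contacts out of 10, with r of 10-30% and D of 10-30, r × D × w/10 (w contacts affected) gives an average visit mean change of 0.1 to 2.7 points. The average per-visit share is 1-9%, against 10-30% who ever react.

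**Noise in a per-subject maximum.** With no withdrawal effect, the change at one assessment has SD σ√2. At σ = 4, P(rise ≥ 10) is 1 − Φ(10/5.66), about 4%. Over 12 assessments sharing one baseline, simulation gives 22% with at least one such rise (7% at σ = 3, 37% at σ = 5). By symmetry the same share show a fall of 10 or more. With 20% reacting for 4 days at σ = 4, the share who ever rise is about 0.20 × 1 + 0.80 × 0.22 = 38%, so the signal is the gap between increases and decreases.

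**Requiring two consecutive rises of 10 or more.** At σ = 4 this flags 22.6% for the 4-day reaction against 4.8% with no effect, but only 5.2% for a 1-day reaction. It measures sustained rises and misses brief ones.

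**The case against.** The best reply is that the SAP already shows much of this. The range of change from Withdrawal Baseline is printed at every window, so the largest individual rise at each contact is visible. In the spread-onset illustration the largest displayed change averages about 35 points, against about 20 from noise alone. By-subject listings are planned (SAP 6.2.1). Per-subject evidence of withdrawal comes from worst-case DESS, from discontinuation-emergent AEs by interval after the last dose (SAP 7.4.2) and from monitored events in the withdrawal period (SAP 7.4.8.3.2). The study is descriptive, with no hypotheses (SAP 6.2.2).

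All of that stands, and it limits the point. It does not close it. A range shows one extreme subject and not how many reacted, and a listing is not a pre-specified summary. The DESS gives one point per new or worsened symptom, whereas the CSSA grades severity.

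Three stronger readings are tempting and not supported.

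- A reader might infer that withdrawal reactions would be invisible in the planned output. That is true at most of means and medians, and even those move clearly if onset clusters.
- A reader might take the absence of the CSSA from the worst-case list in SAP 6.1.5 as further evidence. That list covers only the open-label treatment period. The DESS is not on it either, yet has a worst-case analysis.
- A reader might fault the protocol endpoint at Weeks 53-55. The SAP goes beyond it; the gap lies in SAP 7.4.6.2.

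**Conclusion.** The point holds as a gap in the CSSA summaries, not as lost data or an inability to detect withdrawal. That no planned CSSA table can give the number of subjects who ever rose follows from the text alone and needs no assumption. How much the by-visit tables understate a reaction cannot be fixed from the documents. In the 20%, 20-point, 4-day illustration the largest by-visit mean change runs from about 1.4 to about 3.4 points on a 0-127 scale, depending only on whether onset is spread or clustered. Onset, duration, size of rise, share reacting, noise SD and the 10-point threshold are all assumed. This is a cheap improvement that should be made, and it aligns the CSSA with what the SAP already does for the DESS.

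**What to change.** In SAP 7.4.6.2 add, for the CSSA total score in the withdrawal period:

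- (a) number and percentage of subjects by largest increase from Withdrawal Baseline over all clinic and phone assessments, as for the DESS. Fix the cut-offs, with a reason, before final database lock; an interim data cut has already been analysed.
- (b) the existing score bands at each subject's worst value.

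Denominator: subjects with a Withdrawal Baseline and at least one later CSSA. Report the number of assessments per subject, and show the matching distribution of largest decreases as a noise reference. A count of rises on two consecutive assessments is at most an optional sensitivity table for sustained rises.

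Cost: SAP wording and one table from data already collected. The downside is the noise in a maximum over about 12 assessments (7-37% with a rise of 10 or more at assumed SDs of 3-5, with no effect). The decreases make this visible, with one limit: subjects with low baseline scores cannot fall far before reaching 0, so decreases may understate the noise.
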